8.12 Withdrawal criteria

Participants can choose whether they want to stop using the sbLICBT intervention, or if they want to withdraw from the trial completely (including all assessments) at any time. Participants will also be withdrawn from the trial if the site clinical advisor, or the participant's medical practitioner advises that this is best for their wellbeing. A log will be kept of the participant number, reason for and date of all withdrawals from the trial. Participants who met the inclusion and exclusion criteria at baseline will not be replaced. Participants who did not meet the criteria at baseline can be replaced and their data removed from the data set. Participants who withdraw from the trial will not be followed up. Once a participant withdraws, all email and text notifications that are set on auto will be removed.

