12.4 Summary of baseline data and flow of patients

The analysis and presentation of the trial will be in accordance with CONSORT guidelines (Schulz et al., 2010). Recruitment, intervention uptake, outcome completion rates and attrition will be reported (with 95% Cls) and shown on a flow diagram.

Premature discontinuation of intervention may be instigated by the participant or investigator. Participants may elect to withdraw from the study if they wish to do so at any time and for any reason (including perceived harms or lack of efficacy of intervention). Researchers may also request that trial intervention be discontinued for reasons of participant safety at any time; such requests will be made to and approved by the PI or an appointed deputy where possible.

Participants will be withdrawn from the study entirely if discovered as ineligible at the time of recruitment. As a self-help psychological intervention, we do not anticipate significant iatrogenic effects or side-effects requiring individual discontinuation. Participants who elect to discontinue their allocated intervention will be requested to continue to provide outcome data. If a participant wishes to withdraw from the study entirely (and not provide further follow-up data) we will ask them if they are happy to allow us to retain the data already provided to the trial; if the participant does not consent to retention of data, the data will be destroyed.

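### Participants withdrawn on clinical advice are not followed up under Protocol 8.12, which does not fit with 12.4 and 13.3, so scheduled outcome and adverse event data are not sought from people removed for wellbeing reasons

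*Protocol*

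**What the plan says.** Protocol 8.12 gives the participant two options: stop using the intervention, or leave the trial with all its assessments. For clinical advice it gives one outcome: "Participants will also be withdrawn from the trial if the site clinical advisor" or the participant's own practitioner advises that this is in the participant's interest. It continues: "Participants who withdraw from the trial will not be followed up". It also says: "Once a participant withdraws, all email and text notifications that are set on auto will be removed". What it keeps is a record: "A log will be kept of the participant number, reason for and date of all withdrawals from the trial".

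Protocol 12.4 covers similar ground with a different object: "Researchers may also request that trial intervention be discontinued for reasons of participant safety at any time". Here the intervention stops, not participation. The sentence on continued data reads: "Participants who elect to discontinue their allocated intervention will be requested to continue to provide outcome data". Section 12.4 names two routes out of the study altogether, ineligibility at recruitment and the participant's own wish. Clinical advice is not one of them.

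Protocol 13.3 sets the reporting period for all events and reactions from referral to the 12-week follow-up and says that adverse event data are collected at each assessment. The procedures schedule in 8.11 places adverse event assessments at 6 and 12 weeks. Section 13.1 calls the questionnaires the main indicators of harm.

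**The concern.** Whether someone is still asked for data depends on who initiated the stop and which section staff follow. A participant who chooses to stop the intervention is asked to stay in follow-up. A participant withdrawn on clinical advice is not followed up. A participant stopped at a researcher's safety request falls between the two, because 12.4 does not say whether data are still sought.

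The group that loses follow-up is defined by concern for wellbeing, which is close to what the BRS, PHQ-9, GAD-7 and WSAS measure. Missing data from that group are plausibly related to the missing values. Much of the harm information comes from the same assessments, and under 12.7 the trial may be stopped on cumulative evidence of harm. Attrition and outcome completion are also reported results (12.4) that would inform a definitive trial. Loss imposed by the protocol would be counted with loss through participants' own choice unless the withdrawal log is used to separate them.

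**Working it through.** The protocol states no figure on this point, and 12.1 says there is no sample size calculation, so there is nothing to reproduce. The check is a comparison of the text, followed by an illustration on assumed inputs.

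**Text, by who initiates the stop**

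| Initiator | What stops | Are data still sought? | Source |
|---|---|---|---|
| Participant, intervention only | Intervention | Yes, requested | 8.12, 12.4 |
| Participant, whole trial | Everything | No | 8.12, 12.4 |
| Researcher, for safety | Intervention | Not stated | 12.4 |
| Clinical advisor or own practitioner | Trial participation | No | 8.12 |

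Against the last row, 13.3 requires adverse event reporting to 12 weeks and makes no exception.

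**What depends on the later assessments**

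- The deterioration event in 13.2 needs a PHQ-9 or GAD-7 change from baseline to 6 weeks or from 6 to 12 weeks. Without the later score it cannot be derived.
- 13.3 is narrower about when symptoms count as events, requiring suicidal ideation, plans or an attempt. Those are also asked about on the follow-up website (14.3.2), where the answers serve to monitor suicidality across the arms.
- The schedule in 8.11 has no adverse event assessment other than at 6 and 12 weeks.

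**Illustration**

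Input from the protocol: 120 participants randomised 1:1, so 120/2 = 60 per arm. All other inputs are assumptions.

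*Arm mean.* Suppose k of 60 are removed and would have scored d SD worse than the rest. The observed mean is then too favourable by (k/60) × d.

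| k | d = 0.5 | d = 1.0 | d = 1.5 |
|---|---|---|---|
| 1 | 0.008 | 0.017 | 0.025 |
| 3 | 0.025 | 0.050 | 0.075 |
| 6 | 0.050 | 0.100 | 0.150 |

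*Event proportion.* Suppose a of 60 would have a recorded event and w of those leave before it is recorded. The observed proportion is (a − w)/(60 − w).

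- a = 3 (3/60 = 5.0%): w = 1 gives 2/59 = 3.4%; w = 2 gives 1/58 = 1.7%.
- a = 6 (6/60 = 10.0%): w = 2 gives 4/58 = 6.9%; w = 3 gives 3/57 = 5.3%.

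The shift in means is small unless removals are many. The relative change in event proportions is larger, because a few people make up most of the numerator.

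**The case against.** The two sections need not describe the same event. In 8.12 a clinical advisor or the participant's practitioner advises leaving the trial. In 12.4 a researcher asks, with approval by the principal investigator or a deputy where possible, that the intervention stop. They can be read as two tiers, like the two options that 8.12 offers participants. The no-follow-up sentence also speaks of those who withdraw, not of those who are withdrawn. Both points are fair. But 8.12 has just used the phrase for clinical advice and gives no other rule for that group, and the tiered reading leaves data collection after a researcher's safety stop undefined.

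A reader might infer that harms in this group are lost entirely. The protocol does not support that. The reason for withdrawal is logged (8.12), ongoing SAEs are updated and participant-initiated reports are accepted (13.3), all deaths are reported (13.5), concerns go on a pro forma sent to the sponsor (13.1) and risk alerts go on a register (14.10). The deterioration that prompted the advice is likely to be on record. What is lost is the later scheduled questionnaires and the event questions asked with them.

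A reader might infer that such withdrawals fall mainly in the intervention arm, because on-demand support is one of the routes by which risk is noticed (14.3). That is not shown. The trigger in 8.12 is the advisor or practitioner, assessments and direct contact serve both arms, 8.8 says the action on risk is the same in either condition, and controls receive the intervention after 6 weeks (9.2).

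A reader might infer a departure from intention to treat. The phrase in 8.6 is attached to randomisation. Missing follow-up does not by itself change the arm in which someone is analysed, and the handling of missing data may sit in a SAP that is not at hand.

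Numbers may also be low: entry requires PHQ-9 and GAD-7 of 9 or below (section 7), and 12.4 does not anticipate significant ill effects that would require discontinuation. That limits the size of the problem but does not remove the inconsistency.

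**Conclusion.** The point stands as an inconsistency with a consequence for data. Followed as written, 8.12 ends the scheduled 6- and 12-week outcome and adverse event collection for people withdrawn because of their wellbeing. Section 12.4 limits continued collection to those who choose to stop, and 13.3 assumes reporting to 12 weeks for everyone. The loss begins at withdrawal. For those who leave at their own wish, 12.4 keeps earlier data if they agree.

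That the loss is related to outcome and harm is an inference from the trigger. It is plausible but not demonstrated. Its size is unknown, because the protocol gives no withdrawal or event rate. The illustrated shifts of 0.008 to 0.15 SD in an arm mean, and the falls in event proportion, rest on assumed counts and deficits and show only the order of magnitude. A reader might want to express them as a share of an expected treatment effect, but the protocol states no effect size against which to do so.

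This is not a matter for the SAP: an analysis plan cannot recover data that were never requested. The change should be made, since it is cheap and harm monitoring relies on these assessments. When a participant should stop or leave is a clinical question and is not judged here.

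**What to change.** Reconcile 8.12, 12.4 and 13.3 without altering the clinical grounds for stopping.

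- In 8.12, separate stopping the intervention from ending data collection. State that 6- and 12-week outcome and adverse event data are still requested, whoever initiated the stop, with the participant's consent and unless the clinical advice is against further assessment.
- In 12.4, replace the wording that limits the request to participants who choose to stop with wording that covers discontinuation of the allocated intervention for any reason, including a researcher's safety request.
- In 13.3, say how the 12-week reporting period applies to someone who has been withdrawn, so that it agrees with 8.12.

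The cost is a few sentences. The online assessments already exist. The downside is a small extra contact burden, which the participant can refuse.

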8.13 End of trial

The final follow ups were due in March 2023 (but this has been revised to June 2023) and the project was expected to end June 2023 but this has been revised to February 2024. Any early termination of the trial will be reported to the ethics committee within 15 days.

8.14 Assessment of treatment engagement

Brief questions at 6 week post baseline will assess engagement with the sbLICBT intervention with regards to average frequency and time per week.

9 INTERVENTIONS

9.1 Written Strength-Based Low-Intensity CBT (SBLICBT) Resiliency Intervention with Support on Demand

The intervention is reported according to the Template for Intervention Description and Replication (TIDieR) Checklist (Hoffman et al., 2014).

Table 8 TIDieR Checklist

Item	Description
Brief Name	Bounce Back: Finding Your Inner Strength
Why	As a consequence of being exposed to increasing demands presented by University life, students now have an increased likelihood of experiencing mental health difficulties resulting in long-term disadvantage. Enhancing resiliency to enable students to cope when facing such demands has potential to prevent the development of mental health difficulties. A protocol for a strength-based CBT intervention (Padesky & Mooney, 2012) has informed the development of a written low-intensity CBT intervention. To enhance resiliency, the participant engages with the written intervention to work through four-steps –(1)Record a successful regular activity, (2)Build a personal model of resiliency, (3)Apply personal model of resiliency to an area found challenging, (4)Practice resilience.
What	Written strength-based low-intensity CBT intervention with an initial 60-minute didactic group session to provide an overview of the resiliency intervention and introduce availability of 'on demand' support. On-demand support will be available face to face, virtual, phone or by email for up to 6 weeks.
Who Provided	A Psychological Wellbeing Practitioner (PWP) trained to support the intervention with supervision provided.
How	Following a 60-minute didactic group session where the intervention introduced, participants will be encouraged to engage with the written CBT self-help intervention over the following 6 weeks. 'On demand' minimum contact 'Plan-Do-Review' support will be available on request, over face to face or by email.
Where	University of Exeter.
When and How Much	First delivery from October 2022 (revised to June 2023). Following the initial group session, participants will be encouraged to engage with the intervention on their own over the next 6 weeks. It will be emphasised that engaging for a manageable amount of time on a regular basis is better than trying to use the intervention for a long period of time periodically. However, the exact amount of time the participant engages with the intervention will be determined by them. To recruit 120 participants will require 3 iterations (30 sbCBT and 30DTC) per iteration, with the final DTC group receiving the intervention outside of the study.
Tailoring	The intervention has been co-produced with undergraduate students for a population of university students.
Modifications	The intervention used within the study is a modification of a previous intervention developed for university students. Modifications include removing 'resiliency' from the title and changing to 'Bounce Back', alongside reducing the frequency of the term 'resiliency' in the text itself.
How Well	Fidelity to the email support protocol will be measured by comparing written support emails to a fidelity checklist informed by an e-mail support protocol (Hadjistavropoulos et al., 2018).

9.2 Delayed Treatment Control (DTC)

Participants randomised into the DTC will receive the intervention when those initially randomised into the intervention arm have completed the 6-week intervention.

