8.10 Trial assessments

Assessment will take place at baseline (start of treatment) and then at 6 weeks post baseline (equating to end of treatment) and 12-weeks post baseline. The 3-month follow up will be the primary endpoint. All assessments will be through EXCTU managed EDC system. Only if participants have not responded to email and text prompts to complete their follow ups at 6 and 12 weeks will they be contacted by phone and asked to provide the primary outcome measures only on the telephone. The results of the assessments are only to collect research data for the trial and will not be provided to medical practitioners. The only exception to that would be if a participant indicates suicide risk and asks us to provide their assessment results to their medical practitioner. They would need to give written consent for this and provide us with the contact details to do so. See risk protocol in Appendix.

At the end of treatment, participants that have received the sbLICBT resiliency intervention will receive an email asking them to participate in an acceptability focus group and Section 12 of the protocol provides further information on this.

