10.4 Primary endpoint/outcome

The primary endpoint of the trial is at 12 weeks post baseline.

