10.5 Secondary endpoints

The secondary endpoint is at 6 weeks post baseline (treatment end).

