12.1 Sample size calculation

As a feasibility study with embedded pilot RCT there is no sample size calculation. Rather, data will be used to inform a sample size calculation for any subsequent definitive RCT were the data to demonstrate potential effectiveness.

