12.6 Secondary analyses

12.6.1 12 week post baseline follow-up comparison

Primary (BRS) and secondary (PHQ-9; GAD-7, WSAS) outcomes will be compared at 12 week follow-up using the statistical approach outlined above.

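### The 12-week comparison of clinical outcomes is immediate versus delayed treatment wherever controls have crossed over, yet week 12 is named the primary endpoint

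*Protocol*

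**What the plan says.** Section 8.10 treats baseline as the start of treatment and schedules follow-up at "6 weeks post baseline (equating to end of treatment) and 12-weeks post baseline". For the control arm, 9.2 states: "Participants randomised into the DTC will receive the intervention when those initially randomised into the intervention arm have completed the 6-week intervention". The description of the intervention in 9.1 adds a qualification, "with the final DTC group receiving the intervention outside of the study", without saying when that treatment would happen. The feasibility outcomes table (10.1 and Appendix 1) has a separate block for DTC participants who move to the intervention, so crossover inside the study is planned.

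On timing of endpoints, 8.10 says "The 3-month follow up will be the primary endpoint" and 10.4 says "The primary endpoint of the trial is at 12 weeks post baseline". Section 10.5 ranks the 6-week assessment as secondary. Under 12.6.1, the Brief Resiliency Scale (BRS), PHQ-9, GAD-7 and WSAS "outcomes will be compared at 12 week follow-up using the statistical approach outlined above". Section 12.6.2 covers baseline, 6 and 12 weeks, and reports comparisons between the two conditions to explore effect sizes.

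On the use of the results, 12.1 says that "data will be used to inform a sample size calculation for any subsequent definitive RCT were the data to demonstrate potential effectiveness". Sections 5 and 12.5 make feasibility the primary outcome and, with acceptability, the primary analysis.

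**The concern.** A delayed-treatment design gives a comparison with untreated controls only until the controls are treated. Here that window closes at about week 6, but the time point with the higher rank is week 12. By then the intervention arm is 6 weeks past the end of its treatment, and any DTC participant who crossed over at week 6 is finishing the same 6-week course. A between-arm difference at week 12 then answers whether starting 6 weeks earlier matters, not whether the intervention works.

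The protocol does not say this anywhere. A reader of the eventual report could take a small 12-week difference in BRS as weak evidence of benefit. If that figure were also carried into planning, it would distort the decision on a definitive trial and its size.

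**Working it through.** **1. Timeline**

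| Week post baseline | Intervention arm | DTC that crosses over under 9.2 | Rank in protocol |
|---|---|---|---|
| 0 | starts | waits | – |
| 6 | ends (8.10) | untreated; starts at about this time | secondary (10.5) |
| 12 | 6 weeks after treatment | ends its own 6 weeks (6 + 6 = 12) | primary (8.10, 10.4) |

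Week 6 is the only follow-up at which, by plan, all controls are untreated. Even that has a soft edge: 8.10 allows telephone chasing of non-responders at 6 weeks, and nothing links the date of a DTC questionnaire to that participant's group session.

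**2. Share of DTC treated by week 12**

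Section 9.2 makes no exception, so the share s is 1. Section 9.1 takes the final DTC group outside the study, with no timing. If that group is still untreated at week 12, s depends on the number of iterations, on which the protocol also disagrees:
- 12.2: two iterations, 2 × 60 = 120, giving s = 1/2.
- 9.1: three iterations of 30 + 30, 3 × 60 = 180, giving s = 2/3.
- 8.6: six iterations of 60, 6 × 60 = 360.

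Only the first matches the planned 120. The share cannot be fixed from the document.

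**3. Illustrative dilution**

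The protocol gives no effect size, SD, power or alpha, so there is no figure of its own to reproduce. All of the following are assumptions:
- d: effect at end of treatment against an untreated control, in SD units.
- r: fraction of d kept 6 weeks later.
- g: fraction of d that treated DTC participants have gained by week 12.

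The effect against untreated controls at week 12 would be r·d. The expected observed contrast is d(r − s·g), so it is understated by s·g·d.

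For d = 0.40 and r = 1, with the size that a later trial would need if planned on that contrast, n per arm = 2(1.960 + 0.842)²/contrast² (80% power, two-sided 5%, rounded up, z values carried unrounded):

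| s | g | Contrast (SD) | n per arm |
|---|---|---|---|
| 0 | – | 0.40 | 99 |
| 1/2 | 0.5 | 0.30 | 175 |
| 1/2 | 1 | 0.20 | 393 |
| 2/3 | 0.5 | 0.27 | 221 |
| 1 | 0.5 | 0.20 | 393 |
| 1 | 1 | 0 | none finite |

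With s = 1 and g = 0.5, d = 0.3 becomes 0.15 (698 instead of 175 per arm) and d = 0.5 becomes 0.25 (252 instead of 63). At 90% power, planning on 0.20 instead of 0.40 gives 526 instead of 132 per arm. If benefit fades, the sign can turn: r = 0.75 with s = g = 1 gives 0.40 × (0.75 − 1) = −0.10.

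**4. Precision**

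With 60 per arm, the 95% confidence interval half-width is 1.960 × √(2/60) = 0.36 SD, before attrition and without baseline adjustment. The dilution is a bias on top of this sampling error.

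**The case against.** The strongest reply is that this is a feasibility study. Sections 5 and 12.5 make feasibility primary, Table 10 lists all four scales as secondary outcomes, and Table 11 schedules the feasibility outcomes at 12 weeks only. A 12-week primary endpoint therefore fits the feasibility counts, which crossover does not bias. This stands, and it limits the point to the clinical comparison. It does not remove it: 12.6.1 still compares the arms at 12 weeks and calls BRS a primary outcome, and 8.10 speaks of primary outcome measures collected by telephone, which describes questionnaires.

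Three stronger readings are tempting, and the document does not support them:
- *The pilot cannot supply an effect estimate.* It can. Section 12.6.2 includes the 6-week comparison, and estimates of SD and retention remain usable.
- *The whole control arm has been treated since week 6.* Section 9.1 leaves open that the final DTC group is untreated at week 12.
- *The definitive trial will be sized on the 12-week difference.* Section 12.1 refers only to data, and names neither a time point nor a point estimate. The sample sizes above show what would follow from that use, not that it is planned.

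It is also fair to say that the 12-week contrast is a valid randomised estimate of immediate versus delayed treatment. The fault is in its rank and its missing label.

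**Conclusion.** The point holds for the 12-week between-arm comparison of BRS, PHQ-9, GAD-7 and WSAS. Wherever DTC has crossed over, it does not measure the effect against an untreated control, and it understates that effect if the intervention works. The direction needs only two things: some benefit, and at least one DTC cohort treated before its 12-week assessment. The size cannot be stated from the protocol, because the treated share is unresolved and d, r and g are assumed. Across the illustrations with d = 0.40 and full retention, between a quarter and all of the effect is lost.

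The feasibility outcomes are sound, and the comparison with untreated controls is already scheduled. The defect is that the protocol ranks that comparison below the contaminated one. It should be corrected, but it does not invalidate the trial. Using week 6 removes the bias but not the imprecision of a pilot with 60 per arm.

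**What to change.** - In 8.10, 10.4, 10.5 and 12.6, make week 6 the between-arm comparison for the four clinical outcomes, and name it as the source of any effect size used under 12.1.
- Keep week 12 for the feasibility outcomes. Report clinical outcomes then descriptively, labelled as immediate versus delayed treatment and split by whether DTC participants had been treated.
- Record the date of each DTC 6-week questionnaire relative to that participant's group session, and add a sensitivity analysis that leaves out those completed after it. This exclusion applies to one arm only, so it should support the main 6-week analysis, not replace it.
- Reconcile 9.1, 9.2 and the feasibility outcomes table on which DTC cohorts are treated inside the study and when, and align the iteration counts in 8.6, 9.1 and 12.2.

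The cost is wording, one recorded date and one extra analysis, since both assessments are already scheduled. The downside is that there will be no randomised estimate against an untreated control at 12 weeks. The present design does not provide one either where DTC has crossed over.
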